Secondary arm: Determine the social and technical infrastructure that would be required to rapidly detect and interrupt influenza transmission at the household level; determine whether a home-based self-test and antiviral delivery strategy would be feasible in the context of a pandemic; and assess the prevalence of antiviral resistance in post-treatment nasal swab specimens.

I. Background

Acute respiratory infections (ARIs) are a major cause of morbidity worldwide.¹ In the United States, the estimated annual economic burden of influenza to the healthcare system and society is \$11.2 billion (\$6.3-\$25.3 billion), and the Centers for Disease Control and Prevention (CDC) estimates that influenza has resulted in 140,000-960,000 hospitalizations and 12,000-79,000 deaths annually since 2010.^{2,3} Current influenza prevention and treatment options available to the general population include seasonal vaccination and antivirals for both treatment and prophylaxis. Despite these options, lack of durable immunity and variable influenza vaccine effectiveness contribute to large-scale epidemics each season.⁴⁻⁶ This highlights a need for additional evidence-based prevention and treatment strategies to increase preparedness.

Current Antiviral Receipt Process: Traditionally, influenza infection is diagnosed during a clinic visit and if antiviral treatment is prescribed, a subsequent visit to a pharmacy to receive the antivirals is required. This multi-step process leads to delays in receipt of antivirals and potentially exposes other individuals in clinics and pharmacies to influenza. This practice is problematic since viral shedding occurs during this time frame, and it is well-established that antiviral therapy is most effective when started within 48 hours of symptom onset.⁷⁻¹² Additionally, this process may deter individuals from seeking care and thus further the spread of influenza within households and communities.

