[figure not shown]
II. Study design

This is a pilot study that will evaluate the feasibility of a home-based approach to influenza infection for households in the Seattle, WA area, utilizing an influenza self-test, followed by telehealth consultation for diagnosis and rapid home delivery of antivirals. Households with 3 or more of the same members at least 4 days per calendar week will be eligible to enroll, as long as there are at least 2 members in household eligible to take BXM. Individuals 12 years or older, weighing at least 40 kg, will eligible to take BXM, and thus, are able to enroll as drug eligible participants. Individuals that are not able to take BXM will be able to enroll in the study as drug ineligible participants. Individuals within an eligible household will be enrolled prior to or during the annual influenza season and monitored throughout the influenza season for the development of a cough or 2 or more respiratory symptoms. If a drug ineligible study participant, meaning a household member who does not meet BXM criteria, develops symptoms, they will use an influenza self-test; however, regardless of the result, they will not be able to receive BXM. Nevertheless, the drug ineligible study participant will provide one self-collected or parent/permanent legal guardian-collected nasal swab specimen that will be mailed back to the laboratory for further testing.

If a drug eligible study participant in the household develops a cough or 2 or more respiratory symptoms, he/she will use a prepositioned influenza self-test kit as soon as possible. Additionally, the individual will connect with a healthcare provider through the 98point6 app to

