4. Once connected, the participant will drop the media that has been mixed with the nasal swab sample from the dropper onto the target area of the test strip.

Additional nasal swabs, from a standardized nasal swab kit, will be collected from the participants. For drug ineligible and for drug eligible, participants not diagnosed with influenza, only one nasal swab will be collected at Study day 0 via self-swab or parent/legal guardian-swab. For drug eligible, participants diagnosed with influenza nasal swab specimens will be collected at Study day 0, Study day 2-3, and Study day 5-7 via self-swab or parent/legal guardian-swab following an influenza diagnosis from the telehealth provider. After collection, the swab will be placed directly into a 5 mL tube containing universal transport media (UTM) that is included in the standardized nasal swab kit, and a barcode unique to the participant will be placed on the outside of the tube. Next, the tube will be enclosed in a biohazard bag, then packaged with an absorbent sleeve and placed into one of the provided return shipping boxes, with an attached pre-paid shipping labels. Previous testing has demonstrated that respiratory

viral RNA is stable at room temperature in UTM for up to one week. Nevertheless, these specimens will be placed into the mail as soon as possible so that the nasal swabs can be returned to the laboratory via delivery services the day of or the day after collection for testing and further characterization. This same process for specimen return will occur at Study day 2-3 and Study day 5-7.

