A list of serious adverse events will be presented by shelter and by treatment v. intervention period. As defined in the study protocol, serious adverse events include death, a life-threatening reaction to the study drug (or placebo) or other study procedure, hospitalization, or significant or persistent disability or impairment. The incidence of SAE's (events/person-days of follow-up) will be presented both (1) overall and (2) by case v. non-cases. We will test for a difference in SAE rate between the two study periods (intervention v. control) using an exact Poisson test in R.

Baloxavir-resistant influenza transmission

Evidence of a strong intervention effect causing incidence of baloxavir-resistant influenza strains will be evaluated using linear mixed effects logistic regression. The unit of analysis will be influenza-positive tests, and the outcome will be binary: baloxavir-resistant or not baloxavir-resistant.

B5. Power sample size

Table 1. Sample size calculations: Number of clusters needed per arm for two-group cluster-randomized trial - Household intervention study

Effect size (% reduction in flu incidence)			
Power	0.30	0.40	0.50
0.80	57	84	129
0.90	76	112	172

All calculations above assume an ICC of 0.29, anticipated average (or actual) cluster size of 4, and a 15% transmission rate for flu.

Based on these calculations, an arm size of 250 households should be sufficient to detect a 30% reduction in flu incidence at 90% power.

B6. Endpoint Analyses

Primary Analysis

[figure not shown]
Question: Does this home-based self-test diagnostic tool and rapid treatment intervention lead to a large percentage of influenza-positive individuals initiating antiviral therapy within 48 hours of symptom onset?

Endpoint: Cumulative incidence of influenza virus infection

Measure of Association:
Cumulative Incidence (Attack Rate, Incidence Proportion)

$$\text{Cumulative Incidence} = \frac{\text{Number of participants that successfully initiate antiviral therapy within 48 hours of symptom onset (among participants who have a cough and self-test positive for influenza) during the October 2019-May 2020 influenza season}}{\text{Number of influenza-free participants at risk at } t_0 \text{ (baseline)}}$$

Relevant DAG

Exposure:

Exposed (Treatment) = Participants who develop cough and self-test positive
Unexposed (No treatment) = Participants who develop cough but self-test negative

Outcome:

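### The resistance model in SAP B4 seeks an intervention effect with no comparator, and its per-test outcome does not separate Day 0 resistance from resistance arising after treatment

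*SAP*

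**What the plan says.** The resistance paragraph in SAP B4 (Safety Analysis, under a heading on transmission of resistant influenza) reads: "Evidence of a strong intervention effect causing incidence of baloxavir-resistant influenza strains will be evaluated using linear mixed effects logistic regression". It continues: "The unit of analysis will be influenza-positive tests, and the outcome will be binary: baloxavir-resistant or not baloxavir-resistant". It gives no fixed effects, random effects or comparator.

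The stated targets are these:
- SAP section A, objective S6: emergence of resistance, by sequencing.
- Protocol Summary, secondary aim: "assess the prevalence of antiviral resistance in post-treatment nasal swab specimens".
- Protocol III, secondary endpoints: the proportion with resistance among drug-eligible and drug-ineligible participants, and within-host variation between the first and third swab.

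On design, Protocol II says: "This is a pilot study that will evaluate the feasibility of a home-based approach to influenza infection for households". It describes no randomisation, control arm or control period. The SAP nevertheless refers to one. For serious adverse events B4 says "We will test for a difference in SAE rate between the two study periods (intervention v. control", and B6 defines a comparison group as "Unexposed (No treatment) = Participants who develop cough but self-test negative".

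On sampling, Protocol VI has diagnosed drug-eligible participants swabbed at Day 0, Day 2-3 and Day 5-7. For drug-ineligible participants, and drug-eligible participants not diagnosed with influenza, "only one nasal swab will be collected at Study day 0".

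**The concern.** An intervention effect needs a contrast between people who did and did not receive the intervention, and this study does not supply a usable one. An analyst who follows B4 would have to improvise a comparator. The obvious choice, treated against untreated positives, differs in when and how often people are swabbed, so a difference could reflect sampling alone.

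The outcome also mixes two safety signals. A resistant virus at Day 0 was there before dosing and may have been transmitted. A virus that is susceptible at Day 0 and resistant later points to selection under treatment. The plan's stated targets are mainly the second, while the B4 heading names the first. A binary result per positive test answers neither cleanly.

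The stakes go beyond a secondary table. SAP section C sets a halting threshold for resistance as a share of study participants, and a model that counts tests does not produce that quantity.

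**Working it through.** **Is there a comparator?** Three candidates can be read out of the documents.
1. The control period implied by SAP B4, B6 and C. The protocol has no such period.
2. The SAP B6 unexposed group. These participants are self-test negative, so they contribute influenza-positive samples only when the self-test was falsely negative.
3. Drug-ineligible or undiagnosed influenza-positive participants. They give a Day 0 swab only, so they have no post-baseline sample to set against Day 2-3 and Day 5-7.

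None identifies the effect named in B4.

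**Can the Day 0 swab show emergence?** In Protocol V (Onset of Symptoms), the Day 0 swab is step 2, while dispensing, delivery and ingestion are steps 5 to 8. In that order the Day 0 swab precedes the drug. It cannot show treatment-emergent resistance, yet it counts as a test whenever it is positive.

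**How much could a per-test summary differ from the per-person risk?** The documents give no expected resistance rate, sample size or power for this analysis, so there is no planned figure to reproduce. The anchor count does reproduce: 250 x 0.25 = 62.5, or 63 cases, and 1.96 x 0.5/sqrt(63) = 0.123, against the stated 0.12 (Protocol XI).

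Inputs:
- N = 63 treated cases. This takes every expected confirmed infection as treated, which is generous.
- r = 10% of treated cases develop resistance (assumption).
- a and b = shares of treated cases still influenza-positive at Day 2-3 and Day 5-7 (assumptions, three scenarios).
- Every later positive swab from a case with emergent resistance is resistant, and there is no resistance at Day 0 (assumptions).
- m = Day-0-only positives from other household members: 0, 23 or 72. The last two come from the Protocol II attack-rate table at 25%: 63 x 2 x 0.18 = 22.7 (mean household size 3, low bound) and 63 x 3 x 0.38 = 71.8 (size 4, high bound). Treating all of these as Day-0-only is an assumption.

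Per-test proportion = N x r x (a + b) / [N x (1 + a + b) + m].

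| a / b | m = 0 | m = 23 | m = 72 |
|---|---|---|---|
| 100% / 100% | 12.6/189 = 6.7% | 12.6/212 = 5.9% | 12.6/261 = 4.8% |
| 80% / 40% | 7.56/138.6 = 5.5% | 7.56/161.6 = 4.7% | 7.56/210.6 = 3.6% |
| 50% / 20% | 4.41/107.1 = 4.1% | 4.41/130.1 = 3.4% | 4.41/179.1 = 2.5% |

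The ratio to the true risk runs from 0.67 to 0.25, so the understatement is about 1.5- to 4-fold. Dividing the formula by r leaves (a + b)/(1 + a + b + m/N). The ratio therefore depends on shedding and case mix, not on the resistance risk.

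**What would a per-participant count give?** Illustrative Clopper-Pearson 95% intervals over 63 treated cases: 3/63 = 4.8% (1.0-13.3%), 6/63 = 9.5% (3.6-19.6%) and 13/63 = 20.6% (11.5-32.7%). If only 32 cases had paired sequences, 3/32 = 9.4% (2.0-25.0%). The same three events give about half or double the percentage according to the denominator, so the denominator must be stated.

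**The case against.** The strongest reply is that B4 is under-specified but its approach is not wrong. It names a mixed model. With a person-level random effect and a before/after-drug term, rows per test could use Day 0 as each person's own reference. The heading concerns transmission, for which Day 0 swabs from household members are the informative samples. The protocol already lists a simple proportion with resistance and a first-versus-third-swab comparison. The SAP (October 2019) also predates the protocol version (January 2020) that contains the post-treatment aim.

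Much of this stands, and it limits what can be said. A reader might infer any of the following, and the documents do not support them:
- **That the SAP states it will pool pre- and post-dose swabs.** It does not. Pooling is inferred from the absence of any time or treatment term.
- **That untreated cases always give one swab.** The later swabs follow an influenza diagnosis in a drug-eligible participant, not treatment (Protocol Table 1 and VI). A provider may judge antiviral treatment inappropriate, and later cases in an already treated household cannot receive the drug, so a few untreated cases may be swabbed serially. They are not a valid control: they are unplanned and not randomised, and some may carry the treated case's virus.
- **That the understatement is threefold.** That figure (0.10 x 1/3 = 3.3%) needs all three swabs positive and exactly one resistant. It is one scenario, and B4 specifies a regression, not a crude proportion.
- **That the data cannot measure emergence.** The limit lies in the model as written. The serial swabs allow a paired analysis.

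The reply does not supply the missing comparator. Random effects may absorb within-person correlation, but they do not create a control or define which swabs are post-dose. Emergence is also an objective in the SAP itself (S6), so the difference in dates does not remove the mismatch.

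**Conclusion.** The point holds. B4 seeks an intervention effect that no contrast in this single-group study identifies. That part is wrong as written, not merely short of detail. The per-test binary outcome also fails to separate Day 0 resistance from treatment-emergent resistance, because no sampling-day, treatment-status or Day 0 condition is named. A treated against untreated comparison would be confounded by sampling time and number for most participants.

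The range in the table applies only if results are summarised per test. It rests on the assumed 10% risk, the shedding shares, the household case mix and full persistence of the marker on later positive swabs. It shows the direction and plausible scale and does not predict the trial's result. The issue touches a secondary and safety objective and leaves the primary endpoint unaffected.

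**What to change.** Replace the resistance paragraph in SAP B4 as follows.
1. Drop the intervention-effect model and use one row per participant.
2. Define treatment-emergent resistance as a resistance marker absent at Day 0 and present at Day 2-3 or Day 5-7 in a treated case.
3. Report it with an exact 95% CI over two stated denominators: (a) treated cases with a sequenced Day 0 swab and a sequenced later positive swab, labelled as conditional on continued shedding; (b) all treated laboratory-confirmed cases, labelled as a lower bound because cases without a later sequence count as not detected.
4. Report Day 0 resistance in all influenza-positive participants separately, as possible transmitted resistance.
5. State that positive tests here means sequenced laboratory swabs, if that is what is intended.
6. Reconcile B4 with the halting threshold in SAP section C, which is expressed per participant. Reconcile also the interim resistance analyses in section C with Protocol XI, which plans no interim analysis and reviews resistance at the end of the season.

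Protocol II allows only one treated person per household, so the emergent-resistance table has at most one row per household and the exact interval needs no household adjustment.

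The cost is SAP wording only, with the same swabs and sequencing. The downside is wide intervals, as shown above, and no causal statement about the intervention and resistance.

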Title: Pilot of a Cohort of Households for Influenza Monitoring and Evaluation in Seattle (pCHIMES)

Home-based testing and administration of baloxavir within 48 hours of influenza diagnosis in Seattle, WA

Protocol version: 3.1

Date updated: January 14, 2020

Funding: Anonymous

Trial Sponsor: University of Washington

Role of funders and sponsors:

The funders and sponsors had no role in design of this study.

Summary

Background: Households represent an important location for transmission of influenza. Rapid delivery of antiviral may reduce household exposures to influenza among susceptible individuals.

Design: This study is a pilot study of a home-based approach to influenza infection control, utilizing self-test kits and rapid home delivery of baloxavir (BXM).

Population: Households with at least 3 individuals residing there at least 4 days a week, including at least 2 household members that are eligible to take BXM, will be monitored throughout the influenza season for the onset of a cough.

Study size and duration: This study will be conducted in 250 households in the Seattle, WA area for one influenza season, beginning November 1, 2019 and ending May 1, 2020.

Intervention: Household will self-monitor for onset of a cough or 2 or more respiratory symptoms throughout the influenza season. When symptoms develop in a study participant, the participant will self-test for influenza infection using a prepositioned home-testing kit, as well as collect a separate nasal swab specimen at Study Day 0. Additionally, if eligible, the sick participant will connect with a healthcare provider via the 98point6 app on their smartphone to discuss their respiratory symptoms, and the provider will determine whether antiviral treatment is appropriate. If determined to be a probable influenza illness, the individual will receive a rapid home delivery of BXM, and the ill participant will provide a self-collected nasal swab specimen Study Day 2-3 and Study Day 5-7. For all illness episodes, the ill individual will complete a questionnaire regarding symptom duration and severity, as well as behavioral changes due to illness.

Primary aim: Determine the percentage of drug-eligible, individuals with a diagnosed influenza infection who initiate antiviral therapy within 48 hours of symptom onset.

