Person-to-person transmission: We will use the CDC definition for influenza transmission that refers to the ability of an influenza virus to spread from one person to another, most commonly through large or small droplets containing influenza virus that are expelled when a sick person is coughing or sneezing.

XI. Statistical Analyses

The primary objective is to precisely estimate the proportion of drug eligible individuals with an influenza diagnosis who initiate treatment within 48 hours. We define precision in terms of the width of a 95% confidence interval. The width of a 95% CI will be less than or equal to $\pm 1.96 \cdot 0.5/\sqrt{n}$ where n is the number of individuals who test positive for flu. With 250 households participating and an attack rate of 25% we expect 63 individuals with confirmed influenza infection. This will give a 95% CI for the proportion initiating treatment of ± 0.12 or less.

The proportion of drug eligible individuals receiving the drug and initiating treatment within 48 hours of symptom onset using home-based self-test and delivery methods will be estimated. Binomial regression with log link will be used to calculate the relative risk of receiving and initiating treatment within 48 hours by demographic and clinical factors, including age, sex, race/ethnicity, symptom types, symptom severity, and duration of symptoms. The RR, 95% confidence intervals and p-values will be reported.

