SFS Statistical Analysis Plan
Household Intervention Study
Last Revised 10/8/19

Applicable to the following UW IRB Study Protocols:

Seattle Flu Study (SFS) **(6181)**

Household Intervention Study **(8200)**

Funding:

Brotman-Baty Institute, University of Washington

Table of Contents

A. STUDY OBJECTIVES AND SUMMARY	3
B. FINAL ANALYSIS PLAN	4
B1. ANALYSIS DATASETS	4
B2. BASELINE TABLES AND STUDY CONDUCT	5
Description of the main tables and statistical analyses	5
Study Accrual	5
Baseline Demographic Characteristics	5
Baseline Behavioral Characteristics	5
Baseline Influenza and Respiratory Illness Symptoms	5
Drug adherence	5
Retention	5
Follow-up	5
B3. SAFETY ANALYSIS	5
B4. ENDPOINT ANALYSIS	5
Primary Analysis	5
Secondary Analyses	5
Additional analyses with Influenza virus infection as the Endpoint	5
Additional analyses with other respiratory infections as Endpoints	5
Sensitivity Analyses	5
C1. INTERIM ANALYSIS PLAN	5
Original plan	5

A. Study Objectives and Summary

Purpose: To evaluate the efficacy of a home-based approach to influenza testing in households in order to shorten the time to diagnosis, antiviral delivery, and antiviral initiation and reduce influenza transmission within the household.

Design: This study is an open cohort intervention study with prospective exposure assessment. It is a pilot study of a home-based approach to influenza infection, utilizing self-test kits and rapid home delivery of baloxavir (BXM). All members of all households must be asymptomatic at enrollment.

Population: Households with at least 3 individuals residing there at least 4 days a week, including at least 2 household members that are eligible to take BXM, will be monitored throughout the influenza season for the onset of a cough.

Expected study size: This study will be conducted in up to 1,000 households in the Seattle, WA area.

Study duration: One influenza season, beginning November 1, 2019 and ending May 1, 2020.

Primary aim: Evaluate whether this home-based strategy leads to a large percentage of influenza-positive individuals initiating antiviral therapy within 48 hours of symptom onset.

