Secondary aim: Determine the social and technical infrastructure that would be required to rapidly detect and interrupt influenza transmission at the household level and to determine whether a home-based self-test and antiviral delivery strategy would be feasible in the context of a pandemic.

Primary Objectives:

P1) To measure the proportion of individuals who are initiated on antiviral therapy within 48 hours of symptom onset using home-based self-test to diagnose influenza and home delivery of antivirals.

Secondary Objectives:

S1) Proportion of individuals who test positive for influenza using the home-based test within 48 hours of symptom onset

S2) Proportion of individuals who are delivered antivirals within 48 hours of symptom onset

S3) Symptom duration and severity among cases and household contacts

S4) Viral titer and duration of viral RNA detection among influenza-positive cases

S5) Cost effectiveness, assessed using health resource utilization and school and work absenteeism

S6) Emergence of antiviral resistance, assessed by genetic sequencing of influenza strains

B. Final Analysis Plan

This section describes the main statistical analyses that will be conducted on enrolled households at DSMB meetings and at the end of the study.

B1. Analysis Datasets

The Primary Dataset will consist of all individuals from enrolled households who enroll in the study, comprised of symptomatic (drug-eligible) individuals.

All eligible and enrolled households will be included in the study unless they meet one or more of the following exclusion criteria:

1. Previous documentation of an influenza infection prior to or during the annual influenza season in any household member prior to enrollment

At the participant level, enrolled individuals meeting any of the following criteria will be excluded from analysis (note: their household may still be eligible, as another eligible member of their household may still enroll):

1. The individual's informed consent is determined to be not valid
2. The individual has been double enrolled in the study. In this case, the individual's data will be used once.
3. No symptom questionnaire is collected.

B2. Variable definitions

[See Tables 1a-c for details]

B3. Baseline Tables and Study Conduct

Description of the main tables and statistical analyses

This section describes the main tables and statistical analyses. Metrics will be updated monthly and presented to the DSMB at each meeting.

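### SAP B5 sizes a two-group cluster-randomised comparison of influenza incidence, but the study is a single cohort estimating one proportion, so the 90% power claim describes a property this design does not have

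*SAP*

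**What the plan says.** SAP B5 contains one table, headed "Number of clusters needed per arm for two-group cluster-randomized trial - Household intervention study". Its columns (0.30, 0.40, 0.50) are labelled "Effect size (% reduction in flu incidence", and its rows are 80% and 90% power. The stated inputs are an intracluster correlation of 0.29, a cluster size of 4 and a 15% transmission rate. The conclusion is that "an arm size of 250 households should be sufficient to detect a 30% reduction in flu incidence at 90% power".

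The rest of the plan describes a different study:

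- SAP A, Design: "This study is an open cohort intervention study with prospective exposure assessment". The same paragraph calls it a pilot.
- Protocol II: "This is a pilot study that will evaluate the feasibility of a home-based approach to influenza infection for households in the Seattle, WA area".
- Protocol Summary: "This study will be conducted in 250 households in the Seattle, WA area for one influenza season". SAP A and B6 allow up to 1,000.
- SAP A, objective P1: "To measure the proportion of individuals who are initiated on antiviral therapy within 48 hours of symptom onset using home-based self-test".
- Protocol XI: "The primary objective is to precisely estimate the proportion of drug eligible individuals with an influenza diagnosis who initiate treatment within 48 hours". It justifies the size by confidence-interval width, with 63 expected cases and a half-width of 0.12 or less.

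**The concern.** B5 and the primary objective differ in endpoint (influenza incidence against timely treatment), in number of groups (two against one) and in type of inference (a test against an estimate). B5 is the SAP's only sample-size section, so the SAP gives no precision for the quantity that the study is meant to estimate.

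The risk lies in interpretation. SAP A includes reducing household transmission in the study's purpose, and B6 labels the primary endpoint as influenza incidence. With a 90% power claim alongside, an uncontrolled incidence figure could be taken for the result of an adequately powered comparison.

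**Working it through.** **1. What the B5 table computes.** Inputs from B5: p0 = 0.15, ICC = 0.29, m = 4. The design effect is 1 + (4 − 1) × 0.29 = 1.87. B5 gives no alpha; two-sided 0.05 is assumed because it reproduces the table.

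Clusters per arm = (z_α + z_β)² × [p0(1 − p0) + p1(1 − p1)] / (p0 − p1)² × 1.87/4

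| Column, read as risk ratio | p1 | 80% power: computed / printed | 90% power: computed / printed |
|---|---|---|---|
| 0.30 | 0.045 | 56.7 / 57 | 76.0 / 76 |
| 0.40 | 0.060 | 83.3 / 84 | 111.5 / 112 |
| 0.50 | 0.075 | 128.4 / 129 | 171.9 / 172 |

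All six cells reproduce. The table is a genuine two-group calculation, not a one-sample calculation with a loose title.

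The cells reproduce only if the columns are risk ratios, that is, reductions of 70%, 60% and 50%. Read as labelled, a 30% reduction (p1 = 0.105) needs 401 clusters per arm at 80% power and 537 at 90%, against 57 and 76 printed.

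**2. The 90% claim on B5's own terms.** With 250 households per arm, the effective sample per arm is 250 × 4/1.87 = 534.8. For a 30% reduction:

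- standard error = √[(0.1275 + 0.0940)/534.8] = 0.0204
- z = 0.045/0.02035 = 2.21
- two-sided 0.05: Φ(2.21 − 1.96) = 0.60
- one-sided 0.05, the level given in the SAP B6 model section: Φ(2.21 − 1.645) = 0.71

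At 250 per arm, the smallest reduction detectable with 90% power is about 43% two-sided or 39% one-sided.

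**3. Whether a comparison group exists.** Protocol II and V follow every enrolled household in the same way from enrolment or 1 November. Any drug-eligible member with probable influenza can be offered treatment, if it is judged appropriate and nobody in the household has yet received it. Neither document defines randomisation, a second arm or a control period.

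SAP B6 calls self-test negatives unexposed. That cannot supply a comparator for influenza incidence, because the groups are formed by the test result. With no second group there is no test, and so no power.

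**4. The calculation that fits the primary objective.** Protocol XI uses a half-width of 1.96 × 0.5/√n. The expected n is 250 × 0.25 = 62.5, taken as 63. The attack-rate table in Protocol II, repeated in SAP B6, also gives 50 and 25.

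| Household attack rate | n | 95% half-width at p = 0.5 | Wilson 95% interval at 80% observed (nearest count) |
|---|---|---|---|
| 25% | 63 | 0.123 | 0.68 to 0.88 (50/63) |
| 20% | 50 | 0.139 | 0.67 to 0.89 (40/50) |
| 10% | 25 | 0.196 | 0.61 to 0.91 (20/25) |

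The protocol's 0.12 reproduces. The simple interval fails at high proportions and small n: at n = 25 and p = 0.9, the half-width is 1.96 × √(0.9 × 0.1/25) = 0.118, which puts the upper limit at 1.018.

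These n count one primary case per affected household. The denominator in Protocol III is narrower: drug-eligible people positive on both the self-test and the laboratory test. The values are therefore optimistic for that denominator.

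**The case against.** **The right sizing already exists.** Protocol XI uses precision, and the protocol (14 January 2020) is later than the SAP (8 October 2019). This stands. A reader might infer that the study's size has no justification, and that would be wrong: the fault is in the SAP. The SAP also repeats the expected case counts, though without interval widths.

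**Other SAP text fits B5.** B4 plans a Poisson test between study periods. B6 labels the endpoint as influenza incidence and specifies a Wald test of a risk ratio of 1 between control and intervention. C gives control and intervention event rates, and the software note under B6 names `swCRTdesign`. So B5 is not an isolated slip. But no control period is defined anywhere, so these analyses lack a comparator too. The point reaches beyond B5; it does not go away.

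**The study might be called simply underpowered.** A reader might split the protocol's 250 households into 125 per arm and report 35% power (47% one-sided) for a 30% reduction. No document proposes that split. The SAP's ceiling of 1,000 households, taken as 500 per arm, would give 88% (93% one-sided). Neither figure measures the defect, because more households do not create a comparison group.

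**The formula does not require randomisation.** Correct. A two-proportion formula with a design effect applies to any two independent clustered groups. What is missing here is the second group.

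**Conclusion.** The point holds. B5 supports a comparison that the design does not contain, and power for a reduction in incidence is undefined for this study. The 60% (two-sided) and 71% (one-sided) figures apply only to the hypothetical trial in B5 at 250 per arm, under its stated inputs. They show that the 90% statement fails even there; they are not estimates of this study's power.

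That the study is unrandomised is inferred from the absence of any allocation or control procedure; neither document says so outright. If a control was intended, it has to be defined before any of this text can be used, so B5 cannot stand either way. Correcting the column labels alone would not resolve the point, since B5 would still size a two-group trial.

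**What to change.** - **B5:** delete the table and the 90% power sentence. Put in a one-sample precision statement consistent with Protocol XI: half-widths at p = 0.5 of about 0.12 (n = 63), 0.14 (n = 50) and 0.20 (n = 25). Say that these n are primary cases by household attack rate, and so optimistic for the Protocol III denominator. Specify a Wilson or exact interval for high proportions and small n.
- **B5, design statement:** say that there is no comparison group and that incidence and transmission results are descriptive.
- **Text that relies on the absent comparator:** make the same correction to the Poisson test in B4, the Wald test in B6, the control and intervention event rates in C, and the `swCRTdesign` reference. Editing B5 alone would leave the SAP contradicting itself.

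The cost is SAP wording, with no extra participants or data. The SAP gives up a favourable power claim that the design does not support.
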